Brief Description of Study Procedures	
This is a parallel randomized controlled trial. Eligible patients who consent will be randomized to one of two groups: (1) the intervention group who will be given a Dexcom G6 for CGM, or (2) the control group who will follow their current standard finger-prick protocol via a provided Contour Next ONE glucometer. The CGM group must download the Dexcom G6 and Clarity mobile apps for data capture, whereas the standard of care group will use the Contour Next mobile app for their respective readings.
 
The Dexcom G6 captures real-time, dynamic glucose data every five minutes. Devices used in this study are FDA approved and commercially available.

Primary Endpoint	Hemoglobin A1c (HbA1c) level
Secondary Endpoints	Glycemic variability per mean amplitude of glycemic excursion (MAGE), coefficient of variation of HbA1c, range of HbA1c, frequency of hypoglycemic events, healthcare utilization per count of inpatient/outpatient visits, cost of care, current HEDIS performance on diabetes and behavioral health measures, coding specificity for diabetes, emergency department visit per 1000 rate, overall and for patients with diabetes, and hospitalization per 1000 rate related to
	diabetes, and self-reported behavioral changes (e.g. feeling more empowered to self-manage care, engaged with changing healthcare behaviors, and patient perceptions of the technology).
Analysis Population(s)	Patients with diabetes treated at all Reimagine Primary Care facilities (Avenues Internal Medicine, Cottonwood Family Medicine, Cottonwood Senior Clinic, and Holladay Internal Medicine) from 1 November 2018 to 31 December 2019 will be included in this study.
Benefits	Successful demonstration of CGM will allow patients to manage their condition, which may avoid the highs and lows of glucose monitoring and make patients feel better. This may reduce healthcare utilization and cost for the patients and the healthcare system as a whole. Furthermore, general knowledge on how to engage with patients in remote monitoring pilots will be better understood through this study.
Risks	This study includes recruiting patients and data will be collected. To minimize any breach in of private information the team will store data within the enterprise data warehouse/medical record, REDCap, and on secured mobile applications from Contour Next and Dexcom. While all devices used are FDA approved, there could be challenges for new users when using the new Dexcom G6

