- **Process for Aim 1b:** MAGE is a metric of glycemic variability that can be measured from CGM, but not from infrequent (daily) monitoring. Thus, among CGM patients only, we will measure the six-month longitudinal change in 24-hr average MAGE. Upon computing each CGM patient's daily MAGE, we will use patient-level hierarchical modeling (generalized linear mixed models) to estimate the overall sixmonth longitudinal trend in MAGE.

Specific Aim 1c: Measure longitudinal change in daily coefficient of variation (C_v) of blood glucose in CGM

- **Hypothesis for Aim 1c:** The patient-level daily C_v of blood glucose will decrease over six months of CGM.
- **Process for Aim 1c:** Like that of MAGE, C_v of blood glucose is a metric of glycemic variability that requires near continuous monitoring. Thus, among CGM patients only, we will measure the six-month longitudinal change in daily C_v of blood glucose using the standard equation: $C_v = \sigma/\mu$. Once we have computed each CGM patient's daily C_v of blood glucose, we will use patient-level hierarchical modeling (generalized linear mixed models) to estimate the overall six-month longitudinal trend in C_v of blood glucose. Additionally, we will report the patient- and group-level distributions in daily blood glucose extrema (i.e., minimum and maximum).

Specific Aim 1d: Measure longitudinal change in overall blood glucose range and “time in range” ($\max \text{Range} - \min \text{Range}$) in CGM

- **Hypothesis for Aim 1d:** The patient-level daily blood glucose range will decrease and time in range (which is defined by glucose levels from 70 to 180) will increase over six months of CGM usage.
- **Process for Aim 1d:** Again, like MAGE and C_v , the blood glucose range is a metric of glycemic variability that is most meaningful with near continuous monitoring. So, among CGM patients only, we will measure the blood glucose range for the i th day as $\text{Range}_i = \max \text{HbA1c}_i - \min \text{HbA1c}_i$, and then use patient-level hierarchical modeling (e.g., generalized linear mixed models) to estimate the overall six-month longitudinal trend in HbA1c range.

Specific Aim 1e: Measure the effect of CGM vs. the standard finger-prick protocol on frequency of hypoglycemic events

- **Hypothesis for Aim 1e:** The patient-level six-month reduction in frequency of hypoglycemic events will be greater among those randomized to CGM than that among those randomized to control.

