3.0 STUDY DESIGN

This is a pilot, parallel randomized controlled trial of CGM versus a standard finger-prick protocol among patients with type I and II diabetes treated at Intermountain Healthcare’s Reimagine Primary Care Clinics. Patients will

be eligible if their most recent HbA1c level is $\geq 6.5\%$ and they are either currently using a glucose meter or are prescribed a glucose meter at their index encounter. Upon consent, which will occur within in a private office/room within the Reimagine Care Clinic, patients will be randomized into one of two groups:

- **Intervention group:** CGM using a Dexcom G6 to measure glycosylated hemoglobin levels every five minutes. Patients will be asked to download the Dexcom G6 and Clarity applications (to have access to their real-time data) and be given a link to complete an exit survey in REDCap near the end of their study participation. Data will be sent via Bluetooth and then exported by the Intermountain research team into a Tableau (or similar) dashboard for data analysis/comparison (**Appendix A**)
- **Control group:** A standard finger-prick protocol that will require patients to continue with their daily fingerprick regimen established by their physician. This group will be given a Contour Next One meter to ensure that each patient is receiving the same level of accuracy by the same device. A review by Ekhlaspour et al of 17 glucose meters demonstrated wide variability, with only two devices achieving the 2013 ISO standard (with the most accurate being the Contour Next) [7]. Patients in the control group will be asked to download the Contour Next application which will send data via Bluetooth similar to above. Data will be aggregated, and protected health information removed prior to analysis (by Intermountain Healthcare and Savvysherpa). At the end of the study, patients will be asked to complete a short survey in REDCap about their willingness to participate in future studies (**Appendix A**).

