Randomization will be assigned *a priori* using a random number generator from Microsoft Excel. Sub-Investigator will then transcribe these numbers and order them individually in concealed envelopes and present them to the Research Coordinators to ensure the CRC is blinded. At time of consent the Research Coordinator will hand the patient the earliest numbered envelope to randomize. . Patients in both randomized groups will be given the devices and one month supplies to ensure compliance with the protocol. The Study Coordinator and patient will exchange contact information so that the CRC may resupply the patient with necessary equipment at the end of their month supply. The CRC may meet the patient at their Reimagine Care Clinic or off site for patient convenience. All patients are expected to participate for six months, which is near the minimum duration sufficient to measure clinically meaningful changes in hemoglobin A1c related to gradual behavioral changes (e.g., diet, exercise, insulin administration). Further, each patient will complete 2 mandatory blood draws and one elective blood draw at their designated Reimagine Care Clinic to evaluate HbA1c level changes over the course of the study. Baseline HbA1c must be completed on day of enrollment (± 2 days) which Intermountain Healthcare may choose to cover if not paid for by patient's SOC. An elective blood draw will be considered for data if completed at 3 months (± 1 week) and a third required blood draw upon study completion (± 2 weeks) which the study may also choose to cover if not SOC. 2 weeks from 180 enrollment) which the study may pay for if not covered by patient's SOC. We postulate that those that have a more consistent interstitial glucose profile (which avoid the high peak to valley swings), will have a more pronounced difference in pre and post HbA1c levels. Specific Aim #1 above will help our team understand the relationship between interstitial glucose and HbA1c, along with other outcomes of interest which include weight loss, alterations in diet, change in physical activity, etc.

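### The Aim 1d daily range and the synopsis CV and range endpoints are written on HbA1c, which is drawn only two or three times; they should be written on CGM glucose

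*Combined protocol and SAP*

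**What the plan says.** **Aim 1d (Section 2.0).** The heading names overall blood glucose range and time in range, followed by a parenthesis that subtracts a minimum range from a maximum range. The hypothesis is on glucose. It expects the within-day spread of glucose to narrow and, for the second outcome, states: "time in range (which is defined by glucose levels from 70 to 180) will increase over six months". The process paragraph starts on blood glucose range, but its formula for day i is the day's maximum HbA1c minus the day's minimum HbA1c. It ends with a mixed model "to estimate the overall six-month longitudinal trend in HbA1c range".

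**Aim 1c (Section 2.0).** This is on glucose throughout: "The patient-level daily C_v of blood glucose will decrease over six months of CGM". It also plans to report daily glucose minima and maxima.

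**Synopsis, Secondary Endpoints.** After MAGE the list reads "coefficient of variation of HbA1c, range of HbA1c".

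**How each quantity is measured.** On HbA1c, Section 3.0 says "each patient will complete 2 mandatory blood draws and one elective blood draw". On the sensor, the documents disagree. Section 3.0 describes the intervention as "CGM using a Dexcom G6 to measure glycosylated hemoglobin levels every five minutes", whereas the synopsis says the device captures glucose every five minutes and Section 2.0 says the devices measure interstitial glucose.

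**Statistical section.** Section 7.1 lists MAGE, CV and range as the variability metrics without naming what they are computed on. A sentence ahead of Aim 1 in Section 2.0 says that the aims are framed on HbA1c.

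**The concern.** A within-day range needs at least two values on the same day. HbA1c is not measured that way here, so the Aim 1d formula has nothing to work on. The HbA1c wording appears in the formula, in the modelled outcome, in the synopsis endpoint list and in the sensor description, and the introduction to the aims can be read as endorsing it. It is therefore more than one stray symbol, and Section 7.1 does not settle the matter.

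At stake is whether the secondary endpoints named in the synopsis match what is analysed. If the wording stays, the choice of glucose, HbA1c or converted glucose is left to the analyst, possibly after the data are visible. Time in range has a related gap: the hypothesis predicts an increase, but the process paragraph does not say how it will be analysed.

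**Working it through.** **Inputs**
- HbA1c draws per patient: two mandatory and one elective, so 2 or 3 (Section 3.0). Windows: enrollment ± 2 days, three months ± 1 week, completion ± 2 weeks.
- Follow-up: six months, taken as 180 days.
- CGM readings: one every five minutes (synopsis).
- Conversion quoted in Section 2.0: glucose = 28.7 × A1C − 46.7.

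The plan states no figure that depends on this point, so there is none to reproduce.

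**Step 1. Aim 1d as written.** Taking three months as day 90, the draw windows are within 2 days of day 0, days 83 to 97, and days 166 to 194. They do not overlap, so no day has two planned HbA1c values.
- On a draw day, maximum = minimum, so the range is 0.
- On every other day it is undefined: 180 − 2 = 178 days, or 180 − 3 = 177 with the elective draw.

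The only computable values are two or three zeros per patient, which leaves no trend to model.

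**Step 2. The same endpoint on glucose.** 24 × 60 / 5 = 288 readings per full CGM day. Daily range and daily CV can both be computed, and the planned mixed model can be fitted.

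**Step 3. The synopsis wording, taken over the draws (illustration).** For two draws a and b, range = |b − a|, SD = |b − a| / sqrt(2), and CV = SD / mean.

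| HbA1c values | Range | SD | Mean | CV |
|---|---|---|---|---|
| 9.0, 9.0 | 0 | 0 | 9.0 | 0% |
| 9.0, 8.0 | 1.0 | 0.707 | 8.5 | 8.3% |
| 8.0, 9.0 | 1.0 | 0.707 | 8.5 | 8.3% |
| 9.0, 7.0 | 2.0 | 1.414 | 8.0 | 17.7% |
| 9.0, 8.5, 8.0 | 1.0 | 0.5 | 8.5 | 5.9% |

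With two draws, the range is exactly the absolute change and the CV is that change divided by sqrt(2) times the mean. With two or three draws, maximum, minimum, SD and mean do not depend on the order of the values, so neither metric can separate improvement from worsening.

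**Step 4. Converted readings (illustration).** Inverting the quoted formula gives A1C = (glucose + 46.7) / 28.7.
- Range: the glucose range divided by 28.7, for example (180 − 70) / 28.7 = 3.83. This only rescales it, and the direction of any trend is kept.
- CV: SD / (mean + 46.7), lower than the glucose CV by the fraction 46.7 / (mean + 46.7). At assumed mean glucose of 120, 180 and 210 this is 46.7/166.7 = 28.0%, 46.7/226.7 = 20.6% and 46.7/256.7 = 18.2%.

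**Step 5. Time in range.** The heading's parenthesis is a difference of ranges, which is not a time. The hypothesis supplies workable limits, 70 to 180, without a unit (mg/dL is my reading). The process paragraph defines and models range only. Section 7.1 assigns mixed models to Aims 1b to 1e as a group, but the metrics it names do not include time in range.

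**The case against.** The strongest reply is that glucose was plainly meant. The Aim 1d heading, its hypothesis and the clause just before the formula all say blood glucose. Aim 1c is correct, and the sensor sentence in Section 3.0 is contradicted in two other places. A sensible analyst would use glucose. That is probably so, and it points to the same correction. It does not repair the formula or make the synopsis endpoints agree with the aims.

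Four stronger readings are tempting, and the documents do not support them:
- **All variability endpoints are affected.** They are not. MAGE is a CGM metric, and the Aim 1c CV is defined on daily blood glucose.
- **Time in range is a listed secondary endpoint with no valid definition.** The synopsis does not list it, and the Aim 1d hypothesis defines it adequately. The heading's parenthesis may even have been meant for range alone. What stands is the misplaced notation and the missing analysis.
- **The CGM group would look worse than control because its HbA1c improves more.** That needs a between-group comparison of CV or range over the blood draws. Aims 1b to 1d are confined to CGM patients and are planned as within-patient trends.
- **The CV will be understated by 18% to 28%.** That needs every reading to be converted to HbA1c. No section specifies this, and Section 2.0 prefers direct measurement to approximation. Under conversion the Aim 1d range would in fact be computable.

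It is also fair to say that these are secondary analyses in a study that calls itself a pilot.

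**Conclusion.** The Aim 1d range is wrongly defined as written, and two synopsis endpoints carry the same error. The failure to compute belongs to the Aim 1d daily range and rests on the literal formula and the stated draw schedule. The inability to tell improvement from worsening belongs to the synopsis CV and range, and arises only if someone computes them over the blood draws. The 8.3% example illustrates that reading and does not predict the trial's results. Time in range needs a stated analysis, not a new concept.

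HbA1c change as the primary outcome, the 125 enrolled and 100 analysed, and the power statement do not depend on any of this. The point should be corrected before analysis, but it does not threaten the trial's main conclusion.

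**What to change.** 1. **Aim 1d process:** write Range_i = max glucose_i − min glucose_i over the CGM readings of day i, and model the six-month trend in daily glucose range.
2. **Synopsis:** change the two endpoints to daily CV of glucose and daily range of glucose, both in CGM patients.
3. **Time in range:** define it as the percentage of each day's CGM readings from 70 to 180 mg/dL, stating the unit. Remove the heading's parenthesis or move it to the range. Analyse time in range with its own patient-level mixed model suited to a bounded proportion, and name it in Section 7.1.
4. **Section 3.0:** correct the sensor description from glycosylated hemoglobin to glucose.
5. **Section 2.0 introduction:** limit the sentence about framing the aims on HbA1c to Aim 1a.

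The cost is wording changes in the synopsis and Sections 2.0, 3.0 and 7.1, plus one added model specification. The CGM readings are already being collected, and Aim 1c already plans to report daily glucose minima and maxima. No new data, visits or patients are needed.

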- **Process for Aim 1e:** Measure the patient-level change in rate of hypoglycemic events as the patient-level slope of the six-month linear change in the so-called “intensity” (λ) of the estimated nonhomogeneous Poisson point process. Once we’ve computed each patient’s six-month linear change in λ , we will compare the distributions between randomized groups. Note that the motivation for measuring change in frequency as the slope of λ estimated from a non-homogeneous Poisson process is that it allows us to compare changes in frequency of hypoglycemic events between groups with different modes of monitoring (continuous vs daily).

Aim 2: Assess impact of CGM on healthcare utilization and cost

Specific Aim 2a: Measure the effect of CGM vs. standard finger-prick protocol on healthcare utilization

- **Hypothesis for Aim 2a:** The count of primary care, specialist, and emergency department visits or hospital stays over six months will be fewer among those randomized to CGM than that among those randomized to standard finger-prick protocol.
- **Process for Aim 2a:** For each patient, count their visits to a primary care provider or specialist or emergency department/hospital admission. Next, compare the distributions of visit counts between randomized groups using a Poisson test, aggregated as well as stratified by visit type. Other metrics for evaluating utilization may include: current HEDIS performance on diabetes and behavioral health measures, coding specificity for diabetes, emergency department visit per 1000 rate, overall and for patients with diabetes, and hospitalization per 1000 rate related to diabetes.

Specific Aim 2b: Measure the effect of CGM vs standard finger-prick protocol on cost

- **Hypothesis for Aim 2b:** The total variable cost associated with healthcare services/visits over six months will be fewer among those randomized to CGM than that among those randomized to standard fingerprick protocol.
- **Process for Aim 2b:** For each patient, measure total variable cost of associated healthcare services and visits. Then compare the distribution of costs between randomized groups using the Wilcoxon rank-sum test, a non-parametric analogue of Student’s *t*-test.

Aim 3: Qualitatively understand patient perspective of CGM

Specific Aim 3a: Record patients’ self-reported willingness to participate in a CGM pilot

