3.3.2 Exclusion Criteria

- Patients that are not managing their glucose levels for diabetes (and not advised to use a glucose monitor by their physician)
- Patients that are not treated within the four Reimagine Primary Care clinics
- Patients less than 18 years of age, and 81 years of age and older
- Patients with a diagnosis of dementia
- If the patient is currently using a Continuous Glucose Monitor
- Patients with previous hospitalization for hypoglycemia within the last 18 months
- No access to a mobile phone to download the Dexcom or Contour Next applications
- Patients who are pregnant or planning to become pregnant over the course of their six-month participation

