7.1 Statistical Considerations

The primary analysis (Aim 1a) will measure the intervention effect on the patient-level six-month absolute reduction in mean HbA1c. Since not all patients will have their final HbA1c test at six months exactly, we will estimate each patient's six-month reduction in HbA1c by interpolating/extrapolating from their assessments, given that their HbA1c levels were assessed on at least two occasions: baseline, and >3 months post baseline. Then, among patients with a sufficient number of occasions of HbA1c assessments, we will estimate their sixmonth HbA1c using generalized linear mixed models with patient-level random slopes and intercepts, with appropriate link function and distributional family [8]. The quantitative secondary analyses (Aims 1b-e, 2a-b) will use outcomes related to the longitudinal change in various metrics of glycemic variability (MAGE, C_v , range) as well as the frequency of hypoglycemic events, healthcare utilization, and cost. The secondary analyses will also use longitudinal data analysis to assess whether there is a significant reduction in glycemic variability over six months (Aims 1b-d) among those randomized to CGM, whether there is a significant reduction in hypoglycemic events over six months (Aim 1e) among those randomized to CGM, and to assess whether overall healthcare utilization and costs differ between randomized groups [9]. Accordingly, specific aims 1b-e will rely heavily on longitudinal data analysis within a multilevel/hierarchical framework [10], specifically using generalized linear mixed models. In the sensitivity analyses, provider variability will be accounted for using three-level (provider, patient, occasion), quasi-Bayesian generalized linear mixed models [11]. Finally, the sensitivity analyses exploring HTE will use generalized additive models (GAM) to identify subgroups of patients for whom CGM is likely to have a differential effect [12-13].

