7.2 Sample Size and Power

Based on 2018 data pulled from Intermountain's diabetes registry, we estimate that the four RPC clinics (Cottonwood FM, Cottonwood Sr, Holladay IM, and Avenues IM) will see about 30, 22, 17, and 6 study-eligible, unique patient encounters per month, respectively, yielding up to about 75 recruitable patients per month (up to 225 over three months of enrollment). We estimate that enrolling 125 patients – expecting 20% attrition by the sixth-month follow-up, yielding 100 patients for analysis – would be sufficient to achieve >80% power for the primary analysis (absolute reduction in HbA1c) if the standardized difference d of the effect size is >0.8 (**Figure 2**). Here, the standardized difference d is measured in terms of the difference between the randomized group-level means of six-month changes in HbA1c. So, for example, a standardized difference d in the effect size of 0.8 might be observed if the true effect size is, say, -1 (that is, if the difference between the means is -1) and the standard deviation of change is 1.25. Details of the power analysis will be made available upon request.

[figure not shown]

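### Aim 1e compares one hypoglycemia slope per patient, Section 7.1 points to mixed models but only within the CGM arm, and the two-stage route is less efficient than one model of both arms

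*Combined protocol and SAP*

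**What the plan says.** Section 2.0, Specific Aim 1e, hypothesizes a between-group difference: "The patient-level six-month reduction in frequency of hypoglycemic events will be greater among those randomized to CGM" than among controls. The process has two stages. The first is "Measure the patient-level change in rate of hypoglycemic events as the patient-level slope of the six-month linear change in the so-called" intensity of a nonhomogeneous Poisson process. Once every patient has a slope, "we will compare the distributions between randomized groups". No test or weighting is named, and there is no rule for patients with no events or one event. The section justifies the slope as a way to compare arms that are monitored differently.

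Section 7.0 also treats Aim 1e as a between-group effect. Section 7.1 reads differently. It says that "specific aims 1b-e will rely heavily on longitudinal data analysis within a multilevel/hierarchical framework [10], specifically using generalized linear mixed models", which covers Aim 1e, but it describes the question as "whether there is a significant reduction in hypoglycemic events over six months (Aim 1e) among those randomized to CGM". It gives no arm-by-time term for Aim 1e.

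Section 7.2 sizes the trial for HbA1c only, "expecting 20% attrition by the sixth-month follow-up, yielding 100 patients for analysis". It gives no event rate and no power for hypoglycemia.

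**The concern.** The only between-group method described for Aim 1e is the comparison of patient slopes. The mixed models of Section 7.1 are attached to a different, within-arm question. An analyst could follow either section and report a different result.

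The two-stage route also has a statistical cost. The slope of a linear intensity is an absolute change, so it grows with the patient's event count. Patients with the same proportional fall but different underlying rates therefore have different slopes, and this spread obscures the time trend. Patients with few events sit at or near zero and dilute the contrast. Hypoglycemic event frequency is a listed secondary endpoint. If events are infrequent, a null result from this analysis would be hard to interpret.

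**Working it through.** **Inputs from the documents.** 125 enrolled with 20% attrition gives 125 × 0.80 = 100 analysed (Section 7.2), followed for six months (Section 3.0). That reproduces the plan's only sizing figure. There is none for Aim 1e to reproduce.

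**Assumptions (not in the documents).** 1:1 allocation, so 50 per arm; two-sided 5% level; Wilcoxon test on the slopes; equal detection in both arms; same starting rate; CGM intensity falling linearly by 60%, control flat; patient rates gamma-distributed with variance v = 0.5 to 1.0 around a mean of 1; a control mean of μ = 1, 3, 10 or 25 events in six months.

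**Step 1: the patient slope.** With N events in follow-up T, write λ(t) = (N/T)[1 + θ(2t/T − 1)], −1 ≤ θ ≤ 1. The slope is 2Nθ/T².
- N = 0: the slope is 0.
- N = 1: the likelihood is proportional to 1 + θx with x = 2t/T − 1, so the estimate is θ = +1 or −1. The slope is ±2/T², its sign set only by which half of follow-up held the event. With T = 6 months this is ±2/36 = ±0.056 events per month per month.
- Simulated SD of the slope under a flat rate, in units of 1/T²: 0 at N = 0, 2.0 at N = 1, 4.9 at N = 3, 11.3 at N = 10, 19.1 at N = 30.

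**Step 2: signal against spread.** Control patients have true slope 0. A CGM patient whose starting rate is g times the average has true slope −0.6μg/T². At g = 1 this is −1.8/T² for μ = 3, against a sampling SD of 4.9/T² at N = 3. For μ = 10 it is −6/T², against 11.3/T² at N = 10. Because g varies, true slopes differ between CGM patients even when all have the same 60% fall.

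**Step 3: how many patients have few events.** For a gamma-mixed Poisson count with k = 1/v, P(0) = [k/(k+μ)]^k and P(1) = k[μ/(k+μ)]P(0).
- μ = 3, controls: v = 0.5 gives 0.160 + 0.192 = 35%; v = 1 gives 0.250 + 0.188 = 44%.
- μ = 10, controls: v = 0.5 gives 0.028 + 0.046 = 7%; v = 1 gives 0.091 + 0.083 = 17%.

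**Step 4: power.** The comparator is a log-linear arm-by-time contrast conditional on patient, with errors clustered by patient, standing in for a mixed model. Ranges cover repeated runs of 250 to 500 simulated trials per cell; at 250 the Monte Carlo standard error is at most √(0.25/250) = 0.03.

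| Mean events per patient | Patient slopes, Wilcoxon | One model |
|---|---|---|
| 1 | 0.11-0.15 | 0.22-0.26 |
| 3 | 0.27-0.30 | 0.46-0.53 |
| 10 | 0.70-0.78 | 0.94-0.96 |
| 25 | 0.97-0.995 | 1.00 |

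**Step 5: sensitivity.** In a second set of scenarios (CGM end/start rate ratio 0.5 or 0.33, wider spread between patients, 600 runs each), the loss was 4-14 points at a mean of 1 event, 12-31 at 3, 15-29 at 8 and 1-13 at 25. With a t-test on the slopes it was usually smaller, about 7-27 points at 3 to 8 events. With total events held equal in both arms under the 60% fall, the gap at 3 events narrowed to 14-16 points, so part of the main-scenario gap arises because falling rates also leave CGM patients with fewer events. The single model had more power in every scenario with an effect. With no effect, both methods rejected in about 3-7% of trials.

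**The case against.** The strongest reply is that Section 7.1 already names the right model class. Section 2.0 does not say that slopes are fitted separately or compared without weights. A patient's slope could be predicted from a joint model, as Section 7.1 plans for HbA1c with its random slopes. This stands in part: separate, unweighted fitting is the natural reading, not stated text. It does not remove the point, because Section 7.1 poses only the within-CGM question for Aim 1e and leaves the between-group comparison to Section 2.0.

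A second reply is that part of the gain comes from a change of question. Aim 1e specifies a linear, absolute change, while the comparator estimates a relative change and gives more weight to patients with more events. This stands, and the fix must say so.

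Third, event rate, effect size and test are all assumed. This stands too. The exclusion of "Patients with previous hospitalization for hypoglycemia within the last 18 months" concerns severe events and says little about how many lows a sensor or meter will record.

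A reader might infer that patients with no events or one event add pure noise, or weigh as heavily as patients with dozens. Step 1 shows otherwise: their slopes have the smallest spread. Nor can they be the main cause of the loss at 10 events, where only 7-17% of controls have so few.

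**Conclusion.** The point holds as an unreconciled specification with a likely loss of efficiency. Sections 2.0 and 7.1 do not give one agreed between-group analysis for Aim 1e. The two-stage comparison, read naturally, is valid under the null with equal detection but weaker than one model of both arms. Under the main assumptions the loss is roughly 20 points of power or a little more at 3 to 10 events per patient. At 1 event both analyses are weak. At 25 events there is little loss under the 60% fall, though up to 13 points in the second set of scenarios.

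Two stronger readings are tempting and not supported. One is that the plan demonstrably forfeits much of its power: without an event rate, only the direction is firm. The other is that the plan has no joint model at all: Section 7.1 names the class. Aim 1e is secondary in a self-described pilot, so this should be corrected but does not threaten the primary analysis.

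**What to change.** Make the Aim 1e result the arm-by-time term, with a robust confidence interval, from one log-linear Poisson or negative-binomial mixed model of dated events (or weekly or monthly counts) in both arms, with patient random effects and monitored time as offset. Patients with no events or one event then enter through the likelihood and need no special rule. Rewrite Aim 1e in Section 2.0 and the matching sentences of Section 7.1 so that both describe this between-group analysis; any within-CGM trend can be reported from the same model.

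The cost is SAP wording, since the model class is already planned. The downside to state is that the estimand becomes a relative rather than an absolute change in event rate. That suits Section 2.0's purpose of comparing different monitoring modes: a detection difference that is constant over time cancels on the log scale but not in absolute slopes. In a simulation with the same 40% fall in both arms and CGM recording 3 or 10 times as many events, the slope comparison rejected in 23-27% and 80-92% of trials, against 6-7% for the log-scale model. Detection that drifts over follow-up would not cancel.
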